### 9.2 Patient Disposition

All patients screened and randomised will be accounted for. All post-randomisation discontinuations will be summarised by reason for discontinuation. The number of patients screened and not randomised will be presented.

### 9.3 Protocol Deviations

The criteria for protocol deviations considered major with the implication of data exclusions from the Per Protocol (PP) analysis will be determined prior to database lock and unblinding.

### 9.4 Analysis Sets

#### 9.4.1 Intention-to-Treat Analysis Set

The Intention-to-treat (ITT) analysis set will include all randomised patients with treatment assignment according to the planned randomisation.

#### 9.4.2 Full Analysis Set

The Full Analysis Set (FAS) will consist of all randomised patients with at least one Post-baseline 9-point partial Mayo score value with treatment assigned according to the planned randomisation.

#### 9.4.3 Per Protocol (PP) Analysis Set

The PP analysis set will consist of FAS patients who had no major protocol violations that would impact efficacy analysis with treatment assigned according to the planned randomisation.

#### **9.4.4 Safety Analysis Set**

The Safety analysis set will include all randomised patients who received at least one dose of IMP, with treatment assignment according to actual treatment received.

#### **9.4.5 PK Analysis Set**

The PK analysis set will consist of patients in PK subgroup who have at least one after-dose measurable plasma sample.

### **9.5 Trial Population**

#### **9.5.1 Demographics and other Baseline Characteristics**

Descriptive statistics of demographics and other baseline characteristics will be presented for all patients in the ITT, FAS, PP, and Safety analysis sets by treatment group.

#### **9.5.2 Medical History, Concomitant Medication and Other Safety Evaluations**

Medical history will be coded by system organ class (SOC) and preferred term (PT) using the currently available version of the Medical Dictionary for Regulatory Activities (MedDRA) and summarised for all patients in the ITT, FAS, and Safety analysis sets by treatment group.

The number and percentage of patients with medical history conditions will be summarised by SOC and PT.

### **9.6 Endpoint Assessments**

#### **9.6.1 General Considerations**

Due to exploratory nature of this proof-of-concept trial, statistical testing will be performed both at the one-sided 20% and the one-sided 5% level. However, if the direction of the hypothesis is not self-evident, or two-sided in nature (e.g. testing for an interaction term), two-sided tests will be performed.

Quantitative variables will be described with the number of non-missing values, mean, standard deviation (SD), median, and minimum/maximum values. Qualitative variables will be described with the number and percentage of patients with each qualitative characteristic. Missing values will not be included in the calculation of percentages. All data will be listed by individual patient and study visit.

The efficacy data will be descriptively summarized and used for exploratory purposes only.

The Mayo subscores for stool frequency and rectal bleeding will be calculated as an average based on scores collected from the Patient daily Paper Diary, for up to 5, but at least 3 days prior to each applicable visit. If the patient undergoes bowel preparation for endoscopy any of the days before a visit, the day(s) should be censored from mean stool frequency and rectal bleeding subscore calculations for that visit.

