#### Secondary Endpoints

- Clinical and endoscopic response (decrease from Baseline in full Mayo score  $\geq 3$  and  $\geq 30\%$ , including decrease from Baseline in rectal bleeding subscore  $\geq 1$  or rectal bleeding subscore  $\leq 1$ ) at Week 12.
- Clinical remission at Weeks 4, 6, 8, 10, and 12 defined as a stool frequency subscore = 0, rectal bleeding subscore = 0, and 9-point partial Mayo score  $\leq 1$ .
- Clinical response (decrease from Baseline in 9-point partial Mayo score  $\geq 2$  and  $\geq 30\%$ , including decrease from Baseline in rectal bleeding subscore  $\geq 1$  or rectal bleeding subscore  $\leq 1$ ) at Weeks 4, 6, 8, 10, and 12.
- Mucosal healing defined as Mayo endoscopic subscore = 0 or 1 at Week 12.
- Change from Baseline to Weeks 4, 6, 8, 10, and 12 in 9-point partial Mayo score.
- Change from Baseline to Week 12 in full Mayo score.
- Change from Baseline to Week 12 in modified Mayo score (=full Mayo score excluding Physician's Global Assessment (PGA) subscore).

- Change from Baseline to Weeks 4, 6, 8, 10, and 12 in PGA score.
- FDA-defined remission at Week 12, defined as Stool frequency subscore=0, Rectal bleeding subscore=0, and Endoscopy subscore =0 or 1.
- Immunogenicity: Anti-TJ301 antibodies.
- PK subgroup:  $AUC_{inf}$ ,  $AUC_t$ ,  $\%AUC_{ext}$ ,  $C_{max}$ ,  $t_{max}$ ,  $CL$ ,  $V_z$ ,  $\lambda_z$ ,  $t_{1/2}$ , and MRT (if applicable).
- Peak and trough (pre-infusion) TJ301 serum concentration.

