### **4.4 Withdrawal Criteria**

The patients have the right to withdraw from the trial at any time for any reason, without the need to justify their decision. However, the Investigator should record the reason for the patient's withdrawal, if possible. The Investigator also has the right to withdraw patients.

Patients will be withdrawn in the following circumstances:

- A patient's desire to withdraw for any reason.
- Loss to follow-up (every effort must be made to contact the patient; a certified letter must be sent or phone calls on three separate days must be made).

- An adverse event which, in the opinion of the Investigator and/or Sponsor, necessitates withdrawal.
- A patient's substantial non-compliance (e.g. visits non-compliance) after agreement with the Sponsor.
- The Investigator's opinion that continuing the patient in the trial is not appropriate. The Investigator may withdraw a patient at any time if it is considered to be in the patient's best interest.
- Patients suffering a worsening in disease after Visit 5 are to be withdrawn. Worsening will be defined as an increase from the last visit in Mayo rectal bleeding subscore  $\geq 1$ , over 3 consecutive days. Such worsening should be evaluated by the Investigator and confirmed by endoscopy (no improvement or worse) prior to deciding whether or not to withdraw the patient.

Patients discontinued from the trial will be invited to a Safety Follow-up Visit 35 days (5.8 - 6.6 half-lives of TJ301) after the last dose of IMP as soon as possible after a decision of discontinuation has been taken. At these visits, the Investigator will obtain all the required details and document the date of the premature termination and the main reason in the e-CRF.

In case the patient has withdrawn consent, no new data can be entered into the e-CRF and data are recorded in the medical records only. Correction of previous data entries and/or entering of data related to visits/procedures done prior to but made available after withdrawal of consent (e.g. laboratory results) will be allowed unless the patient disapproves it.

Any withdrawal must be fully documented in the e-CRF and source documents, registered in the e-CRF as discontinued, and followed by the Investigator/Investigative Staff. If the reason for discontinuation is an adverse event, the specific event will be recorded in the e-CRF. Withdrawn patients will not be replaced.

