### **9.6.2 Primary Endpoint**

The primary efficacy endpoint is clinical and endoscopic remission (defined as a full Mayo score  $\leq 2$ , no individual subscore  $> 1$ , rectal bleeding subscore = 0) at Week 12 in the ITT population. This binary outcome (remission status=yes/no) variable will be analysed by a logistic regression model with treatment and the randomisation-stratification factors (prior corticosteroids treatment and consent to participate in PK substudy) as fixed effects and the baseline full Mayo score as covariate. A patient with missing data on the remission status will be assumed to be not in remission. Sensitivity analyses, using different analyses sets and missing data handling, will be detailed in the SAP.

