### **9.6.3 Secondary and Exploratory Endpoints**

All dichotomised secondary endpoints will be analysed using a repeated logistic regression model using Generalized Estimating Equations (GEE) with treatment, the randomisation-stratum, and visit as factors, the respective baseline score as covariate, and allowing for a treatment by visit interaction for the FAS and PP analysis set.

Continuous endpoints (e.g. change from Baseline in 6-point/9-point partial or full Mayo Score) will be analysed using a repeated measures Analysis of Covariance (ANCOVA) model for the FAS and PP analysis set using the same adjustments as above.

Endpoints assessed at only one post-baseline visit will be analysed using the cross-sectional equivalents, i.e. a logistic regression (similar to the primary endpoint) for binary endpoints, and ANCOVA for continuous endpoints (without adjusting for visit, and without a visit by treatment interaction).

If applicable,  $AUC_{inf}$ ,  $AUC_t$ , %ExtrapAUC,  $C_{max}$ ,  $t_{max}$ , CL,  $V_z$ ,  $\lambda_z$ ,  $t_{1/2}$  and MRT for TJ301 after the initial dose at Visit 2 (Week 0) will be calculated by non-compartmental analysis using WinNonlin V7.0 or above.

For all patients, serum peak and trough (pre-infusion) TJ301 concentrations over time will be presented as descriptive statistics.

Exploratory exposure-response modelling of the effect of TJ301 on biomarkers and efficacy assessments may be performed and used for optimisation of dose in future trials.

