## APPENDICES

### Appendix 1 – Calculation of Worsening

For a given day after Visit 4, the daily score for rectal bleeding will be calculated as an average based on scores collected from the Patient daily Paper Diary for 5 days prior to that day. If the patient undergoes bowel preparation for endoscopy during any of these 5 days, the rectal bleeding subscore for those day(s) should be considered missing. In addition, the rectal bleeding subscore will be considered missing for the day of all endoscopies and the day after. The daily score for rectal bleeding will be calculated for all the days until the EoT Visit.

Furthermore, for each day after Visit 4, the change in the daily subscore for rectal bleeding from the most recent visit will be calculated. This change will be referred to as the delta in the daily subscore for rectal bleeding for that day.

Examples:

- Assume that for a patient, Day 30 is between Visit 4 and Visit 5, then the delta in the daily score for rectal bleeding at the Day 30 will be calculated as the change in the daily score for rectal bleeding at Day 30 from the daily score for rectal bleeding at Visit 4 (see Section 7.1.1).
- Assume that for a patient, Day 52 is between Visit 5 and Visit 6, then the delta in the daily score for rectal bleeding at the Day 52 will be calculated as the change in the daily score for rectal bleeding at Day 52 from the daily score for rectal bleeding at Visit 5.

Worsening will be defined as an increase from last visit in Mayo rectal bleeding subscore  $\geq 1$ , over 3 consecutive days. Such a worsening should be evaluated by the Investigator and confirmed by endoscopy (no improvement or worse) prior to decision for withdrawal of patient.

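### Excluding missing values from percentages removes patients withdrawn for worsening from the Week 8, 10 and 12 clinical remission denominators, and less completely from those for clinical response

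*Protocol*

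**What the plan says.** **Rule for percentages.** Section 9.6.1, under Endpoint Assessments, says "Missing values will not be included in the calculation of percentages". The Data Analyses part of the synopsis repeats it.

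**The one exception.** For the primary endpoint, 9.6.2 says "A patient with missing data on the remission status will be assumed to be not in remission". Section 9.6.3 gives no such rule for the by-visit secondary endpoints. For endpoints assessed at one visit only it specifies "a logistic regression (similar to the primary endpoint) for binary endpoints".

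**The endpoints concerned.** One is "Clinical remission at Weeks 4, 6, 8, 10, and 12 defined as a stool frequency subscore = 0, rectal bleeding subscore = 0", together with a 9-point partial Mayo score of at most 1. The other is "Clinical response (decrease from Baseline in 9-point partial Mayo score" of at least 2 points and at least 30%, with a condition on bleeding), at the same weeks.

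**Withdrawal.** Section 4.4 says "Patients suffering a worsening in disease after Visit 5 are to be withdrawn", after evaluation by the investigator and confirmation by endoscopy. Appendix 1 says "Worsening will be defined as an increase from last visit in Mayo rectal bleeding subscore" of at least 1, over 3 consecutive days. Afterwards, "Patients discontinued from the trial will be invited to a Safety Follow-up Visit 35 days" after the last dose. The data list for that visit (6.3) contains no diary review and no Mayo score, and Table 1 shows none at Visit 9. Withdrawn patients are not replaced.

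**Analysis set.** Under 9.4.2, one post-baseline 9-point partial Mayo score is enough to stay in the Full Analysis Set (FAS).

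**The concern.** The protocol itself creates missing data that depend on outcome, and its percentage rule then drops the patients concerned. At Week 12 the primary remission rate would count a withdrawn patient as a failure, while the clinical remission rate would leave the same patient out. The two rates would appear in one report with different denominators and opposite principles.

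These percentages will be read. Section 9.6.1 says efficacy data are to be summarised descriptively. Section 9.1 says that the search for efficacy is not confined to the primary endpoint and that the trial informs the decision on full development. Late-visit rates taken partly from patients selected for not having worsened tend to be too high, and the contrast between arms depends on which arm loses more patients.

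**Working it through.** **Inputs.** 90 patients randomised 1:1:1 and about 20% dropout (9.1); planning rates 10% and 40% (9.1); visit schedule (3.1.2, Table 1); endpoint definitions (2.2); worsening definition (4.4, Appendix 1).

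**1. The plan's own figures.** 72/(1 − 0.20) = 90, as stated. 90/3 = 30 per arm, and 20% of 30 is 6.

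**2. Visits affected.** Visit 5 is Week 6, and Visits 6, 7 and 8 are Weeks 8, 10 and 12. A patient withdrawn between Visits 6 and 7 keeps Week 8 and loses Weeks 10 and 12. This withdrawal rule does not touch Weeks 4 and 6.

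**3. Remission status at withdrawal.** The bleeding subscore at the last visit is at least 0. A rise of at least 1 makes it at least 1. Clinical remission requires 0, so no patient withdrawn for worsening is in clinical remission at that time.

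**4. Response status at withdrawal.** Response is measured from Baseline, so worsening since the last visit does not always exclude it. An example in the order stool frequency, bleeding, physician's assessment: Baseline 3 + 2 + 2 = 7, bleeding 0 at Visit 5, then 1 + 1 + 2 = 4. The bleeding rise of 1 reaches the worsening threshold. The fall from Baseline is 3 points, 3/7 = 42.9%, with bleeding at 1, so response is still met. Most such patients would be non-responders, but not all.

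**5. Effect within one arm.** Suppose r of 30 patients are in remission and w others have been withdrawn for worsening. Section 9.6.1 gives r/(30 − w). Counting them as failures gives r/30. The ratio is 30/(30 − w).

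| w | Ratio |
|---|---|
| 1 | 30/29 = 1.03 |
| 2 | 30/28 = 1.07 |
| 3 | 30/27 = 1.11 |
| 6 | 30/24 = 1.25 |

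The last row treats the whole 20% all-cause dropout as failures lost before the visit. If the patients lost would have done as well as those who stayed, the factor is 1.00. For clinical response the factor lies between 1.00 and 1.25.

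**6. Effect between arms, direction only.** The planning rates belong to the primary endpoint and are borrowed here as an assumption: 3/30 on placebo and 12/30 on drug, a difference of 30.0 points when withdrawn patients count as failures.

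| Withdrawn, placebo / drug | Placebo | Drug | Difference (points) |
|---|---|---|---|
| 6 / 0 | 3/24 = 12.5% | 12/30 = 40.0% | 27.5 |
| 0 / 6 | 3/30 = 10.0% | 12/24 = 50.0% | 40.0 |
| 6 / 6 | 3/24 = 12.5% | 12/24 = 50.0% | 37.5 |

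A second set of assumed counts has 9/30 and 15/30 in remission, a difference of 20.0 points. With 9 withdrawn on placebo and 3 on drug (12 of 60, again 20% overall), the percentages become 9/21 = 42.9% and 15/27 = 55.6%, a difference of 12.7 points. The exclusion can therefore shrink a difference as well as enlarge it.

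**The case against.** The sentence in 9.6.1 can be read as an ordinary tabulation convention. It closes a paragraph on descriptive statistics and sets no missing-data strategy. The comparisons are made by the models in 9.6.3. Section 9 leaves the detail of all analyses to a separate statistical analysis plan. A rule there that assigns failure to withdrawn patients could stand beside 9.6.1, just as the primary rule does in 9.6.2, because a value that has been assigned is no longer missing. Withdrawal is not automatic either, and no worsening rate is given.

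Much of this stands. The point reaches only descriptive percentages of exploratory endpoints, the analysis plan could resolve it, and the ceiling of 1.25 is not an expectation. Counting every missing score as failure would also go too far. Section 7.1.1 makes diary scores missing on bowel-preparation days, on endoscopy days and on the day after, so a patient still in the trial may lack a score for procedural reasons.

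What does not stand is that deferral removes the point. The protocol does not stay silent here. It states a rule with one exception, and an analysis plan that follows it inherits the outcome-dependent denominators.

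Three stronger readings are tempting and are not supported:

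- **The repeated logistic model (GEE) is wrong.** The sentence governs percentages, and silence on missing data in that model is normal for a protocol.
- **The rule favours the drug.** Step 6 shows movement in both directions.
- **The phrase in 9.6.3 denies missing-as-failure to the Week-12-only binary endpoints.** It leaves the matter open and can fairly be read as carrying the primary approach over.

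**Conclusion.** The point holds for the descriptive percentages. Read as written, the protocol omits patients known not to be in remission at withdrawal from the clinical remission denominators at the later visits, and omits a group made up mostly of non-responders from those for clinical response. Importance is minor to moderate: the endpoints are secondary and exploratory, and the primary endpoint keeps its own rule in the ITT population.

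The size cannot be computed from the document. The range in step 5 assumes 30 FAS patients per arm (the FAS may be slightly smaller) and that those withdrawn would not have been in remission at the later visit. Step 6 also assumes the borrowed rates and the split of withdrawals, so it shows direction rather than expected effect. No figure stated in the protocol changes.

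**What to change.** - **9.6.1 and synopsis:** exempt the binary efficacy endpoints from the exclusion of missing values.
- **9.6.3:** state that FAS patients who have discontinued before a visit count as non-remitters or non-responders at that visit, in line with 9.6.2. Name the Week-12-only binary endpoints (clinical and endoscopic response, mucosal healing, FDA-defined remission) as included. Use the same status in the models, so that tables and models agree.
- **Patients still in the trial:** state separately how isolated missed visits and scores lost around endoscopy are handled.
- **Sensitivity analysis:** report observed-case percentages and model results alongside.

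The cost is wording in the protocol and the analysis plan. No new data are needed, and visits, treatment and the withdrawal rule stay as they are. The downside is slightly lower absolute rates, and the few withdrawn patients who still met response are counted as non-responders. The observed-case results will show how much this matters.

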### **9.6.2 Primary Endpoint**

The primary efficacy endpoint is clinical and endoscopic remission (defined as a full Mayo score  $\leq 2$ , no individual subscore  $> 1$ , rectal bleeding subscore = 0) at Week 12 in the ITT population. This binary outcome (remission status=yes/no) variable will be analysed by a logistic regression model with treatment and the randomisation-stratification factors (prior corticosteroids treatment and consent to participate in PK substudy) as fixed effects and the baseline full Mayo score as covariate. A patient with missing data on the remission status will be assumed to be not in remission. Sensitivity analyses, using different analyses sets and missing data handling, will be detailed in the SAP.

### **9.6.3 Secondary and Exploratory Endpoints**

All dichotomised secondary endpoints will be analysed using a repeated logistic regression model using Generalized Estimating Equations (GEE) with treatment, the randomisation-stratum, and visit as factors, the respective baseline score as covariate, and allowing for a treatment by visit interaction for the FAS and PP analysis set.

Continuous endpoints (e.g. change from Baseline in 6-point/9-point partial or full Mayo Score) will be analysed using a repeated measures Analysis of Covariance (ANCOVA) model for the FAS and PP analysis set using the same adjustments as above.

Endpoints assessed at only one post-baseline visit will be analysed using the cross-sectional equivalents, i.e. a logistic regression (similar to the primary endpoint) for binary endpoints, and ANCOVA for continuous endpoints (without adjusting for visit, and without a visit by treatment interaction).

If applicable,  $AUC_{inf}$ ,  $AUC_t$ , %ExtrapAUC,  $C_{max}$ ,  $t_{max}$ , CL,  $V_z$ ,  $\lambda_z$ ,  $t_{1/2}$  and MRT for TJ301 after the initial dose at Visit 2 (Week 0) will be calculated by non-compartmental analysis using WinNonlin V7.0 or above.

For all patients, serum peak and trough (pre-infusion) TJ301 concentrations over time will be presented as descriptive statistics.

Exploratory exposure-response modelling of the effect of TJ301 on biomarkers and efficacy assessments may be performed and used for optimisation of dose in future trials.

## **9.7 Extent of Exposure and Treatment Compliance**

Descriptive summaries of the number of days dosed with study drug will be provided for each treatment group. The summaries will be provided for the Safety analysis set.

## **9.8 Safety**

### **9.8.1 General Considerations**

Safety parameters will be evaluated for the safety analysis data set.

Complete data listings and summary tables will be created for all safety information and include adverse events, concomitant medications, vital signs, clinical laboratory test values, and 12-lead ECG.

For safety data, Baseline will be defined as the last observed value collected prior to the start of treatment. No statistical testing for comparison of treatment groups will be performed for safety variables.

### **9.8.2 Adverse Events**

A pre-treatment adverse event will be defined as an adverse event which occurs between signing the informed consent form and before the first dose of the IMP. A treatment-emergent adverse event (TEAE) will be an adverse event which occurs in the time interval from time of start of the first dose of the IMP up to 28 days after the Follow-up Visit. If an adverse event on Day 0 occurs before administration of IMP, it will be recorded as a pre-treatment adverse event. A post-treatment adverse event is any adverse event occurring after the patient's last visit (see also Section 8.6.2).

Treatment-emergent adverse events will be tabulated by SOC and PT using the currently available MedDRA version. The total number of patients reporting an adverse event, the percentage of patients (%) with an adverse event, and the number of events (E) reported will be presented.

Summary tables will be prepared for:

- All adverse events
- Adverse events by causality (reasonable possible/no reasonable possible)
- Adverse events leading to death
- Adverse events by intensity
- Adverse drug reactions by intensity
- SAEs
- Adverse events leading to withdrawal

A separate data listing will be provided of pre-treatment and post-treatment adverse events.

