### **8.2 Collection and Recording of Adverse Events**

#### **8.2.1 Collection of Adverse Events**

The Investigator must monitor the condition of the patient throughout the trial from the time of obtaining informed consent until the last visit.

The sources of adverse events cover:

- The patient's response to questions about his/her health (a standard non-leading question such as "How have you been feeling since your last visit?" is asked at each visit).
- Symptoms spontaneously reported by the patient.
- Investigations and examinations where the findings are assessed by the Investigator to be clinically significant changes or abnormalities.
- Other information relating to the patient's health becoming known to the Investigator (e.g. hospitalisation).

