### **8.6.2 Collection of Serious Adverse Events with Onset after Last Trial Visit**

If an Investigator becomes aware of an SAE after the patient's last visit (this includes withdrawn patients, Section 4.4), and he/she assesses the SAE to have a reasonable possible causality to the IMP, the case will have to be reported to the Sponsor and CRO, using the contact information, regardless how long after the end of the trial this takes place.

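### Section 9.8.2 puts an adverse event in the 28 days after the Follow-up Visit in both the treatment-emergent and the post-treatment class, in a period when routine collection has ended

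*Protocol*

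**What the plan says.** Protocol Section 9.8.2 sorts adverse events into three classes by onset.

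- **Pre-treatment:** after consent and before the first dose. The Day 0 boundary is settled in words: "If an adverse event on Day 0 occurs before administration of IMP, it will be recorded as a pre-treatment adverse event".
- **Treatment-emergent:** "from time of start of the first dose of the IMP up to 28 days after the Follow-up Visit".
- **Post-treatment:** "A post-treatment adverse event is any adverse event occurring after the" patient's last visit, with a pointer to Section 8.6.2.

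The classes are reported differently. "Treatment-emergent adverse events will be tabulated by SOC and PT", whereas for the other two "A separate data listing will be provided of pre-treatment and post-treatment adverse events".

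Collection is set elsewhere. Section 8.2.1 has the investigator monitor the patient "throughout the trial from the time of obtaining informed consent until the last visit". After that, Section 8.6.2 requires a report when the investigator learns of a serious event and "he/she assesses the SAE to have a reasonable possible causality to the IMP". Section 8.5.1 also asks for deaths in the four weeks following the end of treatment to be reported, whatever their cause.

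The last scheduled visit is Visit 9, the Safety Follow-up Visit, on Day 105 (Section 3.1.2 and Table 1).

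**The concern.** The end of one class and the start of the next are tied to different dates. The treatment-emergent window closes 28 days after the Follow-up Visit, while the post-treatment class opens at the last visit, which for most patients should be that same Follow-up Visit. An event in between has two labels. The paragraph takes care to keep the classes apart at Day 0, so an overlap at the other end does not look intended.

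The overlap also falls where observation changes in kind. Up to the last visit, patients are asked about events at each visit. Afterwards an event reaches the database mainly if it is serious, is judged possibly related and comes to the investigator's notice. Tabulating both periods together mixes systematic and selective ascertainment under one heading.

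Adverse events are a primary endpoint (Section 2.2), and the trial is meant to inform a decision about full development (Section 9.1). The few late events that are captured will tend to be related serious ones, so their class should be settled before unblinding.

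**Working it through.** **Inputs**

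- Last dose on Day 70; Visit 9 on Day 105 (Section 3.1.2).
- End-of-Treatment Visit on Day 84; Visit 9 window of ±2 days (Table 1).
- Treatment-emergent window ends at the Follow-up Visit plus 28 days (Section 9.8.2).
- Half-life 5.3 to 6.0 days (Section 3.1.2).

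**The plan's own figure.** Follow-up Visit minus last dose: 105 − 70 = 35 days. 35 / 6.0 = 5.83 and 35 / 5.3 = 6.60 half-lives, which agrees with the stated 5.8 to 6.6.

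**Length of the overlap**

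- Treatment-emergent end: 105 + 28 = Day 133, which is 133 − 70 = 63 days after the last dose.
- Post-treatment start: the day after the last visit, Day 106.
- Days in both classes: 133 − 106 + 1 = 28.

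| Visit 9 held on | Treatment-emergent end | Days in both classes | Length |
|---|---|---|---|
| Day 103 | Day 131 | 104 to 131 | 28 days |
| Day 105 | Day 133 | 106 to 133 | 28 days |
| Day 107 | Day 135 | 108 to 135 | 28 days |

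The visit window moves the overlap but does not change its length. A patient who stops early and attends the 35-day visit as the last visit has the same 28 days: with last dose on day d, they run from d + 36 to d + 63.

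**No Follow-up Visit.** If that visit never takes place, its date does not exist and the treatment-emergent end cannot be computed. The post-treatment class still opens after the last visit attended.

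**What can be collected in the tail**

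- Routine collection: none, since Section 8.2.1 stops at the last visit.
- Related serious events that become known: yes (Section 8.6.2).
- Deaths within four weeks of the end of treatment (Section 8.5.1): this depends on when treatment ends. Counted from the last dose, 70 + 28 = Day 98, before the tail begins. Counted from the End-of-Treatment Visit, 84 + 28 = Day 112, which covers Days 106 to 112, or 7 of the 28 days.

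The protocol gives no event rates, so the number of events affected cannot be derived.

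**The case against.** **Leave it to the analysis plan.** Section 9 refers all analyses to a separate SAP. That would answer an omission, but here the protocol fixes both definitions and they collide. An SAP that assigns each late event to one class must depart from one of the two sentences.

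**Being in a table and in a listing is no error.** This stands. Section 9.8.1 already calls for complete listings as well as summary tables, and a late event enters the treatment-emergent table once. A reader might infer double counting; the text does not support that. The defect is an undecided class.

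**A window longer than active collection does not contradict Section 8.2.1.** This also stands as a matter of logic, and because collection has stopped the overlap will be nearly empty. It limits the impact. It does not make the pooled events comparable or supply the missing rule.

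Three stronger readings are tempting and should not be made.

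- A reader might fault the other summary tables in Section 9.8.2 for not saying whether they are restricted to treatment-emergent events. That is ordinary SAP detail, and nothing stated there is wrong.
- A reader might count the events in withdrawn patients mentioned in Section 4.4 as a further source for the tail. That provision applies after trial completion, which Section 14.3 defines as the last patient's last visit. On that definition it reaches the tail only for withdrawn patients whose Follow-up Visit fell in the final 28 days of the trial.
- A reader might take the length of the overlap as a measure of effect. It counts calendar days, not events.

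**Conclusion.** Section 9.8.2 is wrong as written, at minor severity. For a patient whose last visit is the Follow-up Visit, the two classes share 28 days (Days 106 to 133 on schedule) with no precedence rule, and those days lie outside routine collection. For a patient without a Follow-up Visit, the treatment-emergent window has no defined end.

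The 28-day figure assumes that the Follow-up Visit is the last visit. An unscheduled visit after it (Section 6.4) would delay the start of the post-treatment class and shorten the overlap.

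The consequence is limited to how a few late events are classified and tabulated. Section 9.8.1 rules out between-group testing of safety variables, and the documents give no ground for expecting a difference between arms. Sample size, power and the efficacy analysis are untouched.

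**What to change.** Use one cut-off date in Section 9.8.2 and carry it into the SAP.

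1. End the treatment-emergent window at the Safety Follow-up Visit, or 35 days after the last IMP dose if that visit does not take place. The 35 days are the protocol's own interval for that visit.
2. Define a post-treatment event as one with onset after that date, shown in the existing separate listing.

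The overlap is then 0 days, and for patients whose last visit is Visit 9 the window matches the collection period. The match is not exact if Visit 9 is missed or an unscheduled visit follows it, but each event still has one class.

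The alternative is to keep the 28 days and start the post-treatment class after them. That also removes the overlap and leaves late related serious events in the table, but it keeps selectively reported events among systematically collected ones. It would still need an end date for patients without a Follow-up Visit.

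The cost is two or three sentences. The downside of the preferred version is that a few late related serious events move from the treatment-emergent table to the listing, where they stay visible. Serious adverse event reporting duties do not change.
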